**Associate Investigators:**

[name], PhD  
Senior Investigator and Associate Scientific Director  
for Translational Research  
NICHD, NIH

[name]  
Assistant Professor of Medicine  
Associate Director, Washington University Metabolomics Facility  
Washington University in St Louis

[name]  
Assistant Professor of Pediatrics  
Division of Pediatric Gastroenterology  
Department of Pediatrics  
Washington University School of Medicine

[name]  
Professor of Pediatrics  
Division of Genetics and Genomics  
Department of Pediatrics  
Washington University School of Medicine

[name]  
Assistant Professor of Ophthalmology and Visual Sciences  
Division of Pediatrics  
Washington University School of Medicine

Study type (check all that apply):

Archived biological specimens/medical information

Natural history; definition of phenotype, genotype/phenotype correlation  
 Prospective linkage/gene identification, NOT providing information to participants  
 Prospective linkage/gene identification, providing information to participants  
 Social science; assessments of knowledge, attitudes and behavior  
 Drugs or devices  
 Gene transfer  
 Other interventions

**Estimated Duration of study:** Four Years

**Subjects:** 12 subjects, 0-1 years of age

**Ionizing radiation:** Medically indicated

## Abbreviations

Abbreviations	Description of Abbreviations
24-OHC	24-(S) hydroxycholesterol
27-OHC	27-hydroxycholesterol
AE	Adverse event
ALP	Alkaline phosphatase
ALT	Alanine aminotransferase
ANC	Absolute neutrophil count
aPTT	activated Partial Thromboplastin Time
AST	Aspartate aminotransferase
AUA	American Urological Association
AUC	Area under the curve
AUC 0-t	Area under the plasma or CSF concentration-time curve from zero (0) hours to time (t)
Caregiver-CGIC	Caregiver-Clinical Global Impression of Change
CFR	Code of Federal Regulations
CKD-EPI	Chronic Kidney Disease Epidemiology Collaboration equation
Clinician-CGIC	Clinician-Clinical Global Impression of Change
Cmax	Maximum plasma concentration
CNS	Central nervous system
CSF	Cerebrospinal fluid
CSS	Clinical Severity Score
CT	Cholestane-3 $\beta$ ,5 $\alpha$ ,6 $\beta$ -triol
CTCAE	Common Terminology Criteria for Adverse Events
DMC	Data Monitoring Committee
DNA	Deoxyribonucleic acid
DPOAE	Distortion Product Otoacoustic Emission(s)
DSC	Dose Selection Committee
ECG	Electrocardiogram
eCRF	Electronic case report form
eGFR	Estimated glomerular filtration rate
EU	European Union
FDA	Food and Drug Administration
GCP	Good Clinical Practice
GCA	Glycine-conjugated trihydroxycholanic acid or Glycine Conjugated Acids
GLP	Good Laboratory Practice
GRAS	Generally regarded as safe
HPBCD	2-hydroxypropyl- $\beta$ -cyclodextrin
hsCRP	C-Reactive Protein High Sensitivity
IC	Intracisternal
ICF	Informed Consent Form
ICH	International Conference on Harmonization
ICV	Intracerebroventricularly
IEC	Independent Ethics Committee
iIND	Investigator Sponsored Investigational New Drug Application
IND	Investigational New Drug Application
IRB	Institutional Review Board
IT	Intrathecal
IUD	Intrauterine device
IV	Intravenous

Abbreviations	Description of Abbreviations
LE/LY	Late endosomal/lysosomal
LGAL3	Galectin 3
Lipid-509	LysoSM-509
LP	Lumbar puncture
LSOs	Lysosomal storage organelles
MITT	Modified intent-to-treat
NCI	National Cancer Institute
NfL	Neurofilament light chain
NICHD	National Institute of Child Health and Human Development
NIH	National Institutes of Health
NOAEL	No observable adverse effect level
NPC	Niemann-Pick disease, type C
NPC/Npc1 and NPC2	Genes that, when mutated, cause NPC phenotypes
NPC1	Niemann-Pick disease, type C1 phenotype
NPC1	Niemann-Pick disease, type C1 cat phenotype
Npc1 or Npc1 -/-	Niemann-Pick disease, type C1 mouse phenotype
OAE	Otoacoustic emissions
PPCS	N-palmitoyl-O-phosphocholineserine
PT	Prothrombin time
PTA	Pure Tone Audiometry
QoL	Quality of life
SAE	Serious adverse event
SC	Subcutaneous
SCr	Serum creatinine
SD	Standard deviation
SE	Standard error
SOP	Standard operating procedure
SPL	Sound pressure level
SUSAR	Serious and unexpected suspected adverse reaction
TUG	Timed up and go
ULN	Upper Limit of Normal
US	United States
$V_{d,ss}$	Volume of distribution at steady-state
VSNGP	Vertical supranuclear gaze palsy

## 1. Précis

Niemann-Pick disease type C (NPC) is a lethal, autosomal recessive, lysosomal storage disorder characterized by neurodegeneration in early childhood and death in adolescence. NPC results from mutation of either the *NPC1* (~95% of cases) or *NPC2* genes. Biochemically, NPC is characterized by the endolysosomal storage of unesterified cholesterol and lipids in both the central nervous system and peripheral tissues such as the liver. Individuals with NPC demonstrate progressive cerebellar ataxia and dementia. Acute cholestatic liver disease is frequently observed in the neonatal/infantile period but subsequently resolves. However, chronic, sub-clinical liver disease persists. Intrathecal 2-hydroxypropyl- $\beta$ -cyclodextrin (HPBCD), also known as adrabetadex () has proven effective in reducing signs and prolonging life in NPC1 animal models, and Phase 1/2a data support efficacy in NPC1 patients. Adrabetadex has also been shown to be effective in treating liver disease in the NPC1 cat.

This Phase 1/2a, open-label, multiple ascending dose, multi-center trial will evaluate whether Adrabetadex administered intravenously is effective in treating acute liver disease in NPC infants. The objective of this study is to determine the safety, tolerability and efficacy of intravenous adrabetadex in NPC disease. The primary endpoint is the efficacy of adrabetadex to reduce plasma levels of glycine-conjugated trihydroxycholanic acid ("bile acid biomarker"), an NPC-specific pharmacodynamic biomarker. Secondary endpoints are assessment of the dose-response relationship for attenuation of liver dysfunction, as determined by reduction in serum transaminases (ALT and AST) and liver size. Exploratory lipid, protein, and inflammatory biomarkers will also be examined. This study will enroll up to 12 subjects (6 subjects per dose level) and evaluate two dose levels (500 and 1000 mg/kg). In the first phase of the study, drug will be administered twice a week for six weeks for a total of 12 administrations. Subjects who demonstrate either a significant reduction in the glycine-conjugated trihydroxycholanic acid biomarker or serum bilirubin (direct bilirubin or direct bilirubin:total bilirubin ratio) will be allowed to crossover into a second open-label phase. In this phase of the study, drug will be administered monthly for six months for a total of six administrations. Serum transaminases (ALT and AST) and an abdominal ultrasound will be obtained at the end of the 6-month open-label extension phase. Efficacy will be assessed by reduction in serum transaminases and reduction in spleen volumes. NPC biomarkers [(cholestane-3 $\beta$ ,5 $\alpha$ ,6 $\beta$ -triol (CT), glycine-conjugated trihydroxycholanic acid (GCA), phosphocholinesterase (PPCS)/lysoSM-509 (Lipid-509), 24(S)-hydroxycholesterol (24-OHC), 27-hydroxycholesterol (27-OHC), and neurofilament light chain (nfL)] will also be obtained at these time points and will be considered exploratory outcome measures.

## 2. Introduction

### 2.1 Niemann-Pick Disease, type C1

Niemann-Pick disease, type C (NPC) is a recessive lysosomal storage disorder characterized by impaired intracellular trafficking and subsequent endolysosomal accumulation of unesterified cholesterol and other lipids in the central nervous system and visceral organs (1). NPC results from mutation of either the *NPC1* or *NPC2* genes, with the vast majority (~95%) of cases due to impaired NPC1 function. Incidence of classical NPC has been estimated to be on the order of 1/89,000-104,000 with potential of a late-onset variant of NPC1 with incidence on the order of 1/36,000 (1, 2). The NPC1 phenotype is heterogeneous with respect to both age of onset and symptom complex. Visceral disease including hepatosplenomegaly and cholestatic jaundice of variable severity can be present in early childhood and is followed by progressive neurological disability (3, 4). Common neurological signs and symptoms include vertical supranuclear gaze palsy, cerebellar ataxia, gelastic cataplexy, seizures and cognitive impairment. An adult-onset variant with prominent psychiatric symptoms has recently been characterized (5). Diagnosis of NPC1 is frequently delayed, but the recent development of a serum-based diagnostic test will facilitate earlier diagnosis (6-8). There are no FDA approved therapies for NPC1, although miglustat (Zavesca®) has been approved for use in the European Union and multiple other countries (9-12) based on a controlled trial and long-term extension studies.

### 2.2 Liver Disease in Niemann-Pick Disease, type C1

In infantile and juvenile forms of the disease, patients frequently present with cholestasis or hepatosplenomegaly. NPC has been reported to be the second most common genetic metabolic disorder with neonatal liver disease (13), and was diagnosed in up to 8% of neonates presenting with intrahepatic cholestasis in one case series (14). In the majority of cases the liver disease becomes subacute, although in other cases the liver disease can progress to liver failure. In the majority of cases, liver inflammation and dysfunction persists, as evidenced by chronic elevations in serum transaminases and abnormal prothrombin (PT) and activated partial thromboplastin (PTT) times. Approximately two-thirds of NPC1 subjects enrolled in the NIH Natural History study (06-CH-0186) have had elevated serum transaminases. Liver disease in NPC can result in a lethal degree of hepatic fibrosis and the chronic disease predisposes to hepatocellular carcinoma (15-18). Although interim analysis of the Phase 1/2a trial data indicates that IT therapy has an impact in slowing neurological disease progression, direct CNS delivery, appears unlikely to have an effect on peripheral disease, based on liver chemistries. In the NPC1 cat model subcutaneous administration of HPBCD 1000 mg/kg biweekly (11 treatments over 21 weeks) reduced serum ALT from ~6-fold elevated to 2-fold elevated (19). This was accompanied by correction of the severe vacuolization of hepatocyte and Kupffer cell cytoplasm observed in untreated cats. In human NPC patients dosed under an individual IND, IV administration of HPBCD (2500 mg/kg biweekly) reduced by ~2-3-fold plasma concentrations of cholestan-3 $\beta$ ,5 $\alpha$ ,6 $\beta$ -triol (20) and its metabolite, trihydroxycholanic acid glycine conjugate (21). Both cholesterol-derived metabolites are NPC disease-specific biomarkers that monitors oxidizable free cholesterol in liver tissue (7). A recently discovered NPC plasma biomarker, lipid-509 (22), has been evaluated in treatment settings.

Taken together, the preclinical and human data suggest that IV HPBCD may be effective in reducing liver inflammation and injury and may prevent the long-term sequelae, such as cirrhosis and risk of hepatocellular carcinoma.

### 2.3 Investigational Product Description

2-hydroxypropyl- $\beta$ -cyclodextrin (HPBCD) is a cyclic polysaccharide that can be used to solubilize hydrophobic compounds such as cholesterol. The potential therapeutic efficacy of HPBCD was first investigated by Camargo et al (23) utilizing a NPC1 mouse model (24, 25), but only slight neurological efficacy was observed. Subsequent studies by Liu et al (26, 27) and Davidson et al (28) demonstrated delayed progression of neurological signs and death in *Npc1* mutant mice. Therapeutic efficacy has also been demonstrated in the feline NPC1 model (19). Only 0.3% of HPBCD crosses the blood-brain-barrier (29), thus necessitating the use of extremely high peripheral doses or direct intrathecal infusion to treat the neurologic signs and symptoms of the disease. A Phase 1/2a trial of intrathecal HPBCD conducted at the NIH Clinical Center and 18-month data suggest significant

stabilization of neurological disease progression. Based on these data, a multicenter, multinational Phase 2b/3 trial of intrathecal HPBCD was initiated in the fall of 2015. With the development of a potentially effective therapy for the neurological aspects of NPC1, consideration needs to be given to the treatment of visceral issues.

HPBCD, a generally regarded as safe (GRAS) substance, is a membrane-impermeant cyclic oligosaccharide with a distinctive truncated cone configuration containing 7 cyclo- $\alpha$ -(1,4)-anhydroglucopyranose units with hydroxypropyl groups randomly substituted onto the C2, C3 and C5 positions of the substituents (Fig. 1). All HPBCD are amorphous mixtures of different isomers, characterized by the degree of substitution, which represents the average of substitution of the hydroxyl with propyl groups per HPBCD molecule. The active drug substance in adrabetadex is KLEPTOSE® HPB parenteral grade, which has an average degree of substitution of 4.34 or on a molar basis  $0.63 \pm 0.01$ .

Cyclodextrins, as well as HPBCDs in general, are used extensively to solubilize pharmaceuticals and various regulatory authorities have approved them as excipients. The therapeutic potential of 2-hydroxypropyl- $\beta$ -cyclodextrin (HPBCD) was discovered when HPBCD, injected systemically to *Npc1*-/- mice beginning at either postnatal day 7 or 21 and continuing every other day, delayed onset of clinical symptoms, reduced intraneuronal cholesterol and glycosphingolipid storage, reduced markers of neurodegeneration, and increased animal survival (27, 28). HPBCD enters cells by the endocytic pathway and is delivered to the endolysosomal storage organelles where unesterified cholesterol accumulates in NPC deficiency.

HPBCD replaces the function of NPC1 protein and promotes transport of the accumulated unesterified cholesterol to the endoplasmic reticulum for esterification by acetyl CoA cholesterol:acyl transferase and subsequent efflux (30, 31). While the precise mechanism of HPBCD action to bypass or replace NPC1 function is not yet defined, HPBCD normalizes intracellular cholesterol trafficking by binding the hydrophobic moieties of cholesterol and other lipids.

[figure not shown]

Figure 1. ADRABETADEX, HPBCD

The pharmacological properties of HPBCD have been extensively studied in *Npc1*-/- mice and *NPC1* cats. The pharmacokinetic properties have been studied in rats, dogs, and the *Npc1*-/- mice and *NPC1* cats. The safety of HPBCD was evaluated in a comprehensive toxicology program conducted by Janssen Research Foundation (Janssen) to support its use as a pharmaceutical excipient. Preclinical toxicology studies included single and repeat-dose toxicity studies, in vitro and in vivo genotoxicity assays, carcinogenicity studies, reproductive and developmental toxicity (Segment I, II and III) studies and special toxicity (local tolerance and mechanistic toxicity) studies. HPBCD has been approved for use as an excipient in oral and intravenous (IV) pharmaceuticals for over a decade. The Sponsor has obtained the rights to reference the Roquette Freres Type IV Drug Master File No. 9420 for HPBCD, the drug substance.

### 2.3.1.1 Acute Toxicity Studies

After a single IV dose of HPBCD mortality occurred in mice at a dose  $\geq 10,000$  mg/kg body weight. The most common clinical abnormality at all dose levels (5,000-20,000 mg/kg body weight) in mice was viscous urine. At lethal doses, typical signs of toxicity included soft feces, sedation, piloerection, clonic convulsions, dyspnea, hypothermia, loss of righting reflex, palpebral ptosis, and tremors. IV doses of 2,000 and 4,000 mg/kg body weight were not lethal in rats but did result in hyperemia. Rats in the 4,000 mg/kg body weight group also were observed with viscous urine, hypotonia, ataxia, and swelling of the ears, nose, and paws. Dogs survived single IV doses of 5,000 mg/kg body weight HPBCD. No clinical abnormalities were noted in the females, but coughing, diarrhea/soft feces, and emesis were observed in the males.

### 2.3.1.2 Repeat Dose Toxicity Studies

Repeat dose studies utilizing IV administration were performed in rats and dogs. Urinary tract changes were present after IV administration and included swollen and granular tubular cells in the kidney, swollen epithelial cells in the urinary bladder and renal pelvis, and vacuolated cortical tubules in the kidney. The no-observed-adverse-effect-levels (NOAELs) in the 3-month IV studies were 50 mg/kg body weight in the rat and 100 mg/kg body weight in the dog. In rats, higher doses (100 and 400 mg/kg body weight) led to reduced body weight gain. Hematological changes and altered serum chemistry were seen at the highest dose (400 mg/kg body weight). Urinary parameters were slightly modified and included increases in white blood cells, cylindrical epithelial cells, occult blood, and granular casts and decreases in specific gravity and creatinine associated with larger urine volume. Adrenal gland, spleen, and kidney weights were increased. Kidneys were pale at necropsy. Histological changes in the liver and lung included increased presence of Kupffer cells in the liver and foamy cells and white stippling in the lung. Following the 1, 2, or 3 months of recovery, most of these changes reverted to normal. After 3 months of recovery, the only remaining abnormalities were slightly elevated liver transaminases (400 mg/kg body weight), pale kidney (100 and 400 mg/kg body weight), swollen epithelial cells in the urinary bladder and pelvic epithelium (all doses levels). The corticotubular changes resolved completely (25 mg/kg body weight), almost completely (50 mg/kg body weight), or were partially reversible (100 and 400 mg/kg body weight). In dogs, IV administration of 400 mg/kg body weight, HPBCD led to transient soft feces and slightly elevated alanine aminotransferase (ALT) and bilirubin or haptoglobin. Macroscopic and microscopic (foamy cells) lung changes were seen as well. All of these changes resolved after 1 month of recovery. At the end of the 3-month recovery, swollen epithelial cells were still present in the urinary bladder and renal pelvis but vacuolated cortical tubules (with swollen lysosomes) were no longer present. Repeat-dose studies extracted from the literature also support these findings (32).

### **2.3.1.3 Reproductive and Developmental Toxicity Studies**

Reproductive function (fertility) was not adversely affected by IV administration of HPBCD in rats. Maternal and paternal toxicity was limited to a slight reduction in body weight. No primary embryo toxicity was noted following IV administration in rats or rabbits. Associated with maternal toxicity, decreased survival and reduced birth weight and body weight evolution of the rat pups were noted at 400 mg/kg/day.. In a 2nd un-dosed generation, all variables were normal. No developmental toxicity was noted in any study.

### **2.3.1.4 Genotoxicity and Mutagenicity**

The genotoxic potential of HPBCD was investigated in Ames tests (*S. typhimurium* and *E. coli*), a mammalian cell assay, chromosome aberration test, micronucleus tests, and deoxyribonucleic acid (DNA) repair tests. No mutagenic potential was evident in any of these studies.

## **2.3.3 Previous Human Experience with Intrathecal HPBCD**

In addition to IV administration of HPBCD, NPC1 patients and study participants have received intrathecal (IT) HPBCD (i.e., delivered into the cerebrospinal fluid). The results of a sham-controlled 1-year study (parts A and B) of up to 1800 mg IT adrabetadex delivered every 2 weeks were announced in 2018 and reported on clinicaltrials.gov. In that study, there was no separation between the treated and sham groups in the coprimary outcomes: the NPC-CSS scale 4 key domains and the CGIC. There were no substantial or significant differences between treatment and sham groups with respect to treatment-emergent adverse events, with the exception of hearing loss, which is an expected AE with IT dosing of HPBCD.

## **2.4 Study Rationale**

As described earlier (section 2.2), NPC1 subjects frequently present with acute cholestatic liver disease in the newborn period. In the majority of cases the liver disease becomes subacute, although in other cases the liver disease can progress to liver failure. The goal of this therapy is to reduce the risk of progressive hepatic damage that results in hepatic fibrosis and need for liver transplantation.

Taken together, the preclinical and human data suggest that adrabetadex administered by the IV route may be effective in reducing liver inflammation and injury and may prevent the severe long-term sequelae, such as hepatic fibrosis, hepatocellular carcinoma, and liver failure that requires transplantation. The safety, tolerability, and clinical efficacy of the drug will be determined in this dose-finding study.

### **3. Study Objectives**

The overall goal of this study is to reduce the risk of progressive hepatic fibrosis due to inflammation in infants with Niemann-Pick Disease, type C. The objectives of this study are to determine the safety, tolerability and efficacy of intravenous adrabetadex in NPC disease following 12 doses given twice weekly for 6 weeks. The primary endpoint is the efficacy of adrabetadex to reduce plasma levels of glycine-conjugated trihydroxycholanic acid ("bile acid biomarker"), an NPC-specific pharmacodynamic biomarker. Secondary endpoints are assessment of the dose-response relationship for attenuation of liver dysfunction, as determined by reduction in serum transaminases (ALT and AST) and liver size. Exploratory lipid, protein and inflammatory biomarkers will also be examined. Subjects who demonstrate significant reduction either in the glycine-conjugated trihydroxycholanic acid biomarker or serum bilirubin (direct bilirubin or direct bilirubin:total bilirubin ratio) will be allowed to crossover into the second phase of the study, an open-label phase of six months duration in which IV adrabetadex will be administered monthly for a total of six doses. Serum transaminases (ALT and AST) and an abdominal ultrasound will be obtained at the end of the six-month open-label extension phase. Efficacy will be assessed by reduction in serum transaminases and reduction in spleen volumes. NPC biomarkers (cholestane-3 $\beta$ ,5 $\alpha$ ,6 $\beta$ -triol, glycine-conjugated trihydroxycholanic acid,PPCS/lipid-509, 24(S)-hydroxycholesterol, 27-hydroxycholesterol, and neurofilament light chain) will also be obtained at these time points and will be considered exploratory outcome measures.

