### 5.4 Eligibility Criteria

#### 5.4.1 Inclusion Criteria

1. Age 0 to 6 months of age at time of enrollment, both genders, and any race/ethnicity.
2. Diagnosis of NPC (either NPC1 or NPC2) based upon meeting any of the two following conditions:
  - A. Two variants classified as pathogenic or likely pathogenic in *NPC1/NPC2* on clinical laboratory testing , or
  - B. One variant classified as pathogenic or likely pathogenic on clinical laboratory testing and a positive NPC biochemical marker (oxysterol or bile acid biomarker or PPCS/Lyo509) test, if acid sphingomyelinase deficiency and cholesterol ester storage disease have been excluded either by clinical molecular testing of the *SMPD1* and *LIPA* genes or by clinical biochemical assay for acid sphingomyelinase and lysosomal acid lipase enzymes (or a combination of enzymatic and molecular testing).
3. Subjects with evidence of NPC-related liver disease as defined by direct bilirubin (DB) >2mg/dL or DB/total bilirubin ratio >0.2.

Variants will be interpreted using the American College of Medical Genetics guidelines for the interpretation of sequence variants and testing must be performed by a CLIA-certified laboratory.

4. Ability to travel to a research site.
5. Willing to participate in all aspects of trial design including serial blood collections.
6. Parent / guardian must provide written informed consent to participate in the study. Because of the age range intended for inclusion, assent will not possible.

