# **6. Assessments, Procedures, and Testing**

## **6.1 Medical History and Physical/Neurological Examinations**

A medical and medication history will be obtained and a physical exam will be conducted after admission to the study center. This will ensure that the subject's medical health is adequate to participate in this study.

Subjects will be evaluated with an interim history and physical examination at least daily while admitted to the study center.

Anthropomorphic measures including weight and height will be obtained weekly in phase 1 and monthly in phase 2.

Physical and neurological examinations will be standardized.

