## **6.4 Abdominal Ultrasound**

In phase 1, an abdominal ultrasound exam will be conducted at baseline and 6 weeks to determine liver size and spleen volumes. Liver size is determined by the liver's midclavicular longitudinal diameter (34). Organ volumes are the product of three long axes (longitudinal, transverse and anterior-posterior) (35). At the time of this abdominal ultrasound in phase 1, liver elastography will also be obtained. In Phase 2, an abdominal ultrasound with liver elastography will be repeated at the end of the six-month protocol.

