## 9. Study Procedures and Schedule

### 9.1 Overview of Study

Subjects who have been screened for eligibility will be admitted to the Neonatal Intensive Care Unit or the Pediatric Intensive Care Unit depending on age for inpatient baseline qualification assessments after written informed consent has been obtained. In phase 1 of the study, the first admission will last approximately 7 days. Subjects may then be followed as outpatients for the subsequent five weeks, or they may remain inpatient if clinically indicated. Upon initiation of the study, a PICC line or other intravenous access will be placed and baseline laboratory testing and liver/spleen ultrasound will be obtained. Drug will be administered twice a week with an interval of  $4 \pm 1$  days. A total of 12 doses will be given. Subjects who demonstrate significant reduction either in the glycine-conjugated trihydroxycholanic acid biomarker or serum bilirubin (direct bilirubin or direct bilirubin:total bilirubin ratio) will be allowed to crossover into the second phase of the study, an open-label phase of six months duration. In this phase of the study, dosing frequency will be monthly with IV adrabetadex for six months for a total of six administrations. Subjects will be evaluated at each study visit for evidence of adverse effects.

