### 9.2 Outline of Protocol Admissions and Testing

Time	Major Events	Admission Type	Length
Phase 1			
Week 1	Enrollment and consent PICC/IV line placement Liver/spleen ultrasound Obtain baseline laboratory testing Administration of 1 st and 2 nd dose	Inpatient	7 days
Weeks 2-6			
Weeks 2-6	Administration of doses 3-12 Obtain laboratory testing	Outpatient*	10 days
Week 6	Liver/Spleen ultrasound PICC line removal	Outpatient*	1 day
Week 7	Post-dose safety evaluation	Outpatient*	1 day
Phase 2			
Month 1	Initiation of open-label extension one month $\pm 7$ days month after dose 12 Obtain baseline laboratory testing Administration of dose 13	Outpatient*	1 day
Months 2-6	Administration of doses 14-18 Obtain laboratory testing	Outpatient*	1 day
Month 6	Liver/Spleen ultrasound Post-dose safety evaluation	Outpatient*	1 day

\*May be performed as inpatient if the patient remains hospitalized

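### The spleen half of the extension efficacy criterion uses raw volume in growing infants, so growth biases the within-subject change towards missing benefit

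*Combined protocol and SAP*

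**What the plan says.** Sections 1 and 3 give a two-part efficacy criterion for the extension: "Efficacy will be assessed by reduction in serum transaminases and reduction in spleen volumes". Section 6.4 defines the measurement: "Organ volumes are the product of three long axes". Scans are taken at baseline and week 6 in phase 1. For the extension, "In Phase 2, an abdominal ultrasound with liver elastography will be repeated at the end of the six-month protocol"; no scan is scheduled at extension entry.

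Section 5.4.1 admits infants with "Age 0 to 6 months of age at time of enrollment". Section 6.1 provides body-size data: "Anthropomorphic measures including weight and height will be obtained weekly in phase 1 and monthly in phase 2". No section links those data to organ size, whether as volume per kg, a multiple of expected volume, a z-score or a growth covariate. No section says whether change is measured from the pre-treatment or the week-6 scan.

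Section 10 does not name spleen volume. It mentions abdominal ultrasound in general terms as a possible guide to an effective dose. It also says that the trial should show which outcome measures respond to treatment and should inform power calculations for a later trial.

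**The concern.** A healthy infant's spleen grows with the infant. If efficacy is read as a fall in raw volume over more than half a year of infancy, the change combines drug effect with growth, and without an untreated group the growth cannot be subtracted. Within a subject the error runs against the drug: a moderate real response can be recorded as no change or as a larger spleen.

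What is at stake is how the trial informs its successor. A responsive spleen measure could be dropped, or too small an effect could be carried into the next power calculation. Transaminases, the other half of the criterion, are not organ volumes and are not affected in this way.

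**Working it through.** The plan gives no effect size, SD, threshold or power for spleen volume, so there is no stated figure to reproduce.

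**Follow-up time.** Inputs:
- Section 9.1: "Drug will be administered twice a week with an interval of" 4 ± 1 days, 12 doses. Eleven intervals of 3 to 5 days put dose 12 on day 33 to 55 after dose 1.
- Outline of Protocol Admissions and Testing: "Initiation of open-label extension one month" ± 7 days after dose 12, that is 23.4 to 37.4 days (one month = 30.4 days).
- Section 9.9: six monthly doses over six months. The last scan falls between dose 18 (5 months after dose 13, 152.2 days) and the end of month 6 (182.6 days).

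Shortest: 33 + 23.4 + 152.2 = 209 days, 6.9 months. Longest: 55 + 37.4 + 182.6 = 275 days, 9.0 months. From the week-6 scan, taken about 2 days after dose 12: (23.4 + 152.2 - 2) to (37.4 + 182.6 - 2) = 174 to 218 days, 5.7 to 7.2 months.

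**Growth model.** Let r be the weight ratio between scans, b the exponent relating normal spleen volume to weight, and f the true size-adjusted fall.
- Observed change in raw volume = r^b × (1 - f) - 1.
- Fall needed before raw volume drops at all = 1 - r^(-b).
- The sign reverses when r > (1/(1 - f))^(1/b).

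The documents give neither r nor b. The assumed values are r = 1.2, 1.5 and 2.0, and b = 1.0 and 0.7.

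| | r = 1.2 | r = 1.5 | r = 2.0 | Sign reverses above |
|---|---|---|---|---|
| Break-even fall, b = 1.0 | 16.7% | 33.3% | 50.0% | – |
| Break-even fall, b = 0.7 | 12.0% | 24.7% | 38.4% | – |
| True 20% fall, b = 1.0 | -4.0% | +20.0% | +60.0% | 1.25-fold |
| True 20% fall, b = 0.7 | -9.1% | +6.3% | +30.0% | 1.38-fold |
| True 40% fall, b = 1.0 | -28.0% | -10.0% | +20.0% | 1.67-fold |
| True 40% fall, b = 0.7 | -31.8% | -20.3% | -2.5% | 2.07-fold |

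Example: r = 1.5, b = 0.7 gives 1.5^0.7 = 1.328, and 1.328 × 0.80 - 1 = +6.3%.

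**Does volume per kg solve it?** With no drug effect, per-kg volume changes by r^(b - 1) - 1. At b = 1.0 this is zero. At b = 0.7 it is -5.3%, -11.5% or -18.8% for the three growth ratios, which would look like benefit.

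**Liver length.** Section 6.4 says "Liver size is determined by the liver's midclavicular longitudinal diameter". A length grows roughly as r^(1/3). For an assumed 1.1- to 1.2-fold weight gain by week 6, the drift is 3.2% to 6.3%.

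**The case against.** The strongest reply is that the consequence is limited. Spleen volume is half of one extension criterion. It is neither a primary nor a secondary endpoint, has no threshold or test, and governs no dosing, entry or stopping decision. Scans, weight and height are all collected, so any index can be computed later. This stands, and it limits the weight of the point. It does not remove it: if the scale is chosen after open-label data have been seen, raw, per-kg and expected-size measures can disagree even in sign.

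It can also be said that Section 6.4 describes how volume is measured, not how change is expressed, and that the documents never call the measure absolute. That is fair; the raw reading follows from the formula and from the absence of any scaling. Next, every growth figure is assumed, and the model takes a storage-enlarged spleen to grow in proportion to a normal one, which nothing in the documents establishes. So the direction of the within-subject bias is secure, but its size is not. Finally, adjustment has its own risk: with a poorly chosen scale, growth alone can look like benefit, as the per-kg figures show.

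A reader might infer that the comparison of the 500 and 1000 mg/kg cohorts is compromised too. The documents do not support that as a main point: dose-response is specified for transaminases and liver size, and no cohort comparison of spleen volume is planned. If one were made with no dose effect, and growth were spread log-uniformly over 1.2- to 2.0-fold with b = 1.0, chance alone would put the ratio of geometric mean fold changes at 0.85 to 1.18 (95% range) with six extension entrants per cohort, or about 0.79 to 1.26 with three. That is chance variation, not systematic bias.

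**Conclusion.** The point holds for the within-subject spleen change in the extension. As written, the plan reads a raw volume over about 7 to 9 months from the first dose, or about 6 to 7 months from week 6, in infants enrolled by 6 months of age, with no untreated group and no size adjustment. Growth biases that reading towards missing benefit. Under the assumed 1.2- to 2.0-fold weight gain, a true 20% fall reads anywhere from -9% to +60%, depending on growth and scaling. A true 40% fall is mainly understated and changes sign only in the fastest-growth case with b = 1.0.

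Two stronger readings should be resisted. A reader might infer that extension efficacy as a whole cannot be assessed, but transaminases are the other half of the criterion. A reader might also infer that the sign will reverse, but how often it would cannot be determined from the documents. The practical harm is a misinformed choice of outcome measures for the next trial, so this should be corrected but is not critical.

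**What to change.** In Sections 1, 3, 6.4 and 10, define one spleen measure: the change from the pre-treatment scan in the log of spleen volume relative to the volume expected for body size, using the weight nearest each scan. Name the reference for expected volume before any scan is analysed. Check that its volume formula matches Section 6.4: an ellipsoid formula carries a factor π/6 = 0.524, so mixing it with a bare product of axes would inflate the level about 1.9-fold (1/0.524), although change from baseline would be unaffected.

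Report volume per kg and absolute volume as sensitivity analyses, not as the measure itself. Expressing liver length relative to body length is optional, because the week-6 drift is small.

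The cost is wording and minor analysis work, with no new visits, scans or samples. The downside is that the result depends on the chosen reference and on weight, which includes the enlarged organs; the sensitivity analyses make that dependence visible.
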